4.2 Design Diagram

This is a Phase 3, multicenter, open-label extension (OLE) study which comprises a 40-week open-label period designed to evaluate the long-term efficacy, safety, and tolerability of adalimumab. 252 adult subjects who participated and successfully completed Study M14-115 Induction were enrolled into this study.

Subjects were evaluated for entry into Study M14-347 at the final study visit (Week 12) of Study M14-115. A subject's participation in the study was anticipated to be up to

40 weeks. There was a \pm 3-day window for all study visits. An effort was made to bring the subject back to their original study visit (calculated from Week 0) if they were out of the visit window.

Study visits for clinical and safety assessments were performed at Weeks 0, 8, 16, 24, 32 and 40/Premature Discontinuation (PD). All subjects were provided with a paper subject diary in which they could record CD-related symptoms (number of liquid or very soft stools, abdominal pain rating, and general well-being) and adalimumab dosing information throughout the study. Blood samples were collected at various time points for routine labs, along with hs-CRP, adalimumab serum concentrations, anti-adalimumab antibody (AAA) levels and other biomarker analyses. In addition, stool samples for calprotectin and microbiota were collected. The stool samples were taken before starting bowel preparations for endoscopy. Endoscopic evaluation were performed at Week 40/PD, if the PD occurred after Week 24. CDAI evaluations were calculated based on entries recorded into the subject's diary at all study visits. The SFPS (Stool [liquid/soft] Frequency + Abdominal Pain Score) were calculated using the weighted values for the CDAI components "Number of liquid or very soft stools" and "Abdominal pain."

All subjects received open-label adalimumab 40 mg every other week (eow) beginning at Week 0. No dose was administered at Week 40. Subjects might be escalated to adalimumab 40 mg every week (ew) at or after Week 1 should the subject met the criteria for inadequate response ([Table 1](#)).

[figure not shown]
Table 1. Inadequate Response

| Response Type | Definition |
|---------------------|---|

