| Inadequate response | Crohn's disease activity index (CDAI) of ≥ 200 at any one visit and at least one of the following criteria is met: an increase of at least 1 mg/L in level of high-sensitivity C-reactive protein (hs-CRP) from Baseline or an hs-CRP ≥ 5 mg/L. The hs-CRP results used to determine inadequate response can be from the prior or current visit. Assessment of inadequate response should include consideration by the Investigator to rule out symptoms caused by reasons other than Crohn's disease related inflammation. |

For subjects taking corticosteroids at Baseline of Study M14-115 adalimumab dose escalation was considered in lieu of increases in steroid dose. Subjects who continued to experience inadequate response on 40 mg ew who were taking corticosteroids at Baseline of Study M14-115 might have their steroid dose increased, per the Investigator's discretion, in order to manage the subject's symptoms. Any subject who continued to experience inadequate response on 40 mg ew might be discontinued from the study at the investigator's discretion after discussion with the study designated physician (SDP).

Subjects who dose escalated to adalimumab 40 mg ew, had one opportunity to de-escalate adalimumab dose to 40 mg eow provided the following criteria had been met: CDAI < 200 and high-sensitivity C-reactive protein (hs-CRP) value equal to or lower than that observed at the time of dose escalation. Subjects who experienced inadequate response after dose de-escalation (using the same criteria outlined above), might again be escalated to 40 mg ew. A subject had only one opportunity to dose de-escalate and one opportunity to re-escalate to ew adalimumab dosing.

Changes in adalimumab dosing might only occur when the above criteria were met but were not mandatory. A schematic for dose adjustments is presented in [Figure 1](#).

Figure 1. Dose Adjustment Algorithm

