8.0 Patient Disposition

The number of subjects will be tabulated by country, investigator site and overall for the following sets:

- ITT analysis set
- Safety analysis set
- Subjects who completed study
- Subjects who prematurely discontinued study drug

In addition, the number and percentage of subjects who discontinued study drug will be summarized by primary reason and by any reason as recorded on the eCRF:

- Adverse event (AE)
- Withdrew consent
- Lost to follow-up
- Lack of efficacy
- Requires alternative (or prohibited) therapy
- Subject non-compliance
- Other

Subjects may have more than one reason for discontinuing study drug, but they will be counted once for the total number of discontinuations. Subjects have only one primary reason for discontinuing study drug or discontinuing from the study.

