- Change in European Quality of Life 5 Dimensions (EQ-5D) from Study M14-115 Baseline over time.
- Change in CDAI from Study M14-115 Baseline over time.
- Change in SFPS from Study M14-115 Baseline over time.
- Change in Abdominal Pain Rating Scale score from Study M14-115 Baseline over time.
- Change in each CDAI component subscore (number of liquid or very soft stools, abdominal pain rating, general well-being, CD related complications, anti-diarrhea use, abdominal mass, hematocrit, body weight) from Study M14-115 Baseline over time.
- Time to first dose escalation.

- Proportion of subjects who require weekly dosing at Week 1 of Study M14-347.
- Proportion of subjects with major CD related event (e.g., hospitalization, bowel surgery, abscess drainage).
- Proportion of subjects with CD related hospitalization.
- Proportion of subjects with CD related surgery.
- Proportion of subjects requiring dose escalation to weekly dosing during this study.
- Proportion of subjects with no draining fistulas over time among subjects with draining fistula at Study M14-115 Baseline.
- Proportion of subjects in each treatment group with > 50% reduction from Baseline of Study M14-115 in the number of draining fistulas over time among subjects with draining fistula at Study M14-115 Baseline.
- Resolution of extraintestinal manifestations over time.
- Proportion of subjects who achieve symptomatic remission, defined as average daily stool frequency ≤ 1.5 (and not worse than Study M14-115 Baseline) and average daily abdominal pain ≤ 1.0 (and not worse than Study M14-115 Baseline) over time among subjects with Study M14-115 Baseline average daily stool frequency ≥ 2.5 or average daily abdominal pain ≥ 2.0 .
- Proportion of subjects who achieve symptomatic remission, defined as average daily stool frequency ≤ 2.8 (and not worse than Study M14-115 Baseline) and average daily abdominal pain ≤ 1.0 (and not worse than Study M14-115 Baseline) over time among subjects with Study M14-115 Baseline average daily stool frequency ≥ 4.0 or average daily abdominal pain ≥ 2.0 .
- Proportion of subjects who achieve symptomatic response, defined as average daily stool frequency at least 30% reduction from Study M14-115 Baseline and average daily abdominal pain not worse than Study M14-115 Baseline or average daily abdominal pain at least 30% reduction from Study M14-115 Baseline and average daily stool frequency not worse than Study M14-115 Baseline, over time.

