For categorical additional efficacy endpoints, the two-sided 95% confidence interval for the proportions will be provided. The NRI method will be used for subjects with missing data at the time point evaluated. The LOCF method will also be used as the sensitivity analyses.

For continuous additional efficacy endpoints, change from Study M14-115 Baseline will be summarized by descriptive statistics using mean, standard deviation, minimum, median and maximum. Both LOCF and observed case analyses will be performed.

For time to event additional efficacy endpoints, the number of event and the 25th, median, and 75th percentiles of time to event will be estimated by the product limit method. The 95% CI for the median time-to-event will also be provided if applicable.

The time to first occurrence of event will be calculated as (first occurrence of event date or censoring date – date of first dose of the treatment during this study + 1). Subjects who did not experience the event prior to discontinue or complete the study will be censored at the date the last assessment was taken. For the endpoint of time to dose escalation, subjects without experiencing an event will be censored at the last available dose date.

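### SAP 10.3 censors subjects who stop study drug on every-other-week dosing in the Kaplan-Meier analysis of time to first dose escalation, so as a description of the treated subjects the percentiles come out too early, by an amount that depends on rates the documents do not give

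*SAP*

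**What the plan says.** SAP 10.3 lists "Time to first dose escalation" among the additional efficacy variables. It is the only time-to-event variable in that list. The SAP plans that "the 25th, median, and 75th percentiles of time to event will be estimated by the product limit method", and adds for this endpoint: "For the endpoint of time to dose escalation, subjects without experiencing an event will be censored at the last available dose date". The rule does not separate subjects who finish treatment on eow from subjects who stop early on eow.

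Four other places bear on the point:

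- SAP 4.2 starts every subject on 40 mg eow, so all are at risk of escalation from Week 0. It also says "Changes in adalimumab dosing might only occur when the above criteria were met but were not mandatory".
- Protocol 5.4.1 gives subjects who stop early a Premature Discontinuation visit, followed by care at the investigator's judgment. No return to study dosing is described.
- SAP 8.0 lists lack of efficacy and "Requires alternative (or prohibited) therapy" among the reasons for discontinuation.
- SAP 10.3 also reports a crude measure: "Proportion of subjects requiring dose escalation to weekly dosing during this study".

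Neither document names discontinuation as a competing event or plans a cumulative incidence estimate. Neither says that the target is the time to escalation had nobody stopped.

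**The concern.** Escalation is a change in study-drug dosing, so it cannot occur once a subject has left study drug. For that subject the event has become impossible; it has not merely gone unobserved. Product-limit censoring nevertheless lets those who remain stand in for the stoppers, as if the stoppers would have escalated at the same rate. The resulting curve can only equal or exceed the actual cumulative share escalated, and its percentiles can only be equal or earlier.

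The natural use of this endpoint is to describe how soon, and in how many subjects, eow maintenance is intensified. A reader will take a reported median as the time by which half of the treated subjects had escalated. Under this rule a median can be reported although fewer than half ever do.

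The censoring may also be informative. Escalation is optional and lack of efficacy is a listed reason for stopping, so subjects doing poorly on eow can leave without escalating.

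**Working it through.** **No figure to reproduce.** The documents state no expected escalation rate, stopping rate or percentile, and SAP 4.3 has no sample size calculation. The check compares the planned estimator with one that counts stopping as a competing event, over a range of assumed rates.

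**Inputs from the documents.** 252 subjects enrolled (SAP 4.2). All start on eow (SAP 4.2). The last eow dose is at Week 38 (Protocol 5.5.1), so completers on eow are censored at about T = 38 weeks.

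**Assumed.** e = share who escalate by Week 38; d = share who stop on eow first; constant cause-specific hazards.

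**Formulas.**

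- Total cumulative hazard: H = −ln(1 − e − d).
- Weekly hazards: h1 = H·e/[(e+d)·T] for escalation, h2 = H·d/[(e+d)·T] for stopping.
- Planned analysis: 1 − KM(T) = 1 − exp(−h1·T), with p-th percentile −ln(1−p)/h1.
- Cumulative incidence: F(t) = h1/(h1+h2) × [1 − exp(−(h1+h2)t)], with p-th percentile −ln[1 − p(h1+h2)/h1]/(h1+h2). It is not reached if this exceeds T.

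**Example 1: e = 30%, d = 15%.** H = −ln(0.55) = 0.5978. Escalation part: 0.5978 × 30/45 = 0.3986, so h1 = 0.01049 and h1+h2 = 0.01573 per week.

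- 1 − KM = 1 − exp(−0.3986) = 32.9%, against 30%.
- KM 25th percentile: 0.2877/0.01049 = 27.4 weeks.
- Cumulative-incidence 25th percentile: −ln(1 − 0.25 × 1.5)/0.01573 = 0.4700/0.01573 = 29.9 weeks.

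**Example 2: e = 45%, d = 20%.** H = −ln(0.35) = 1.0498. Escalation part: 1.0498 × 45/65 = 0.7268, so h1 = 0.01913 per week.

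- 1 − KM = 1 − exp(−0.7268) = 51.7%, against 45%.
- KM median: 0.6931/0.01913 = 36.2 weeks. The cumulative incidence ends at 45%, so its median is not reached.

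**Range.** SE is the standard deviation of 1 − KM over 1,500 simulated trials of 252 subjects.

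| Escalate / stop first | 1 − KM | Shift | Shift in SE | 25th percentile, KM vs cumulative incidence (weeks) |
|---|---|---|---|---|
| 30% / 5% | 30.9% | 0.9 points | 0.3 | 29.6 vs 30.4 |
| 25% / 10% | 26.5% | 1.5 points | 0.5 | 35.5 vs 38.0 |
| 30% / 15% | 32.9% | 2.9 points | 0.9 | 27.4 vs 29.9 |
| 40% / 20% | 45.7% | 5.7 points | 1.7 | 17.9 vs 19.5 |
| 45% / 20% | 51.7% | 6.7 points | 1.9 | 15.0 vs 16.2 |

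At 5% stopping the shift stays at or below 0.5 SE for escalation from 20% to 50%.

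**When KM reports a median although under half escalate.** The stopping share has to exceed about 6% (16 of 252) at 48% escalating, 16% (40) at 45%, 25% (62) at 42%, or 31% (77) at 40%. At 35% it would take about 44% (111), so nothing appears at 35% or below for stopping up to 30%. In 500 simulated trials per scenario, a KM median with a crude share under half occurred in 64% at 45%/20%, 34% at 48%/10% and 0% at 30%/15%.

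**Sensitivity to hazard shape.** Hold 45%/20% and the stopping hazard constant, but make the escalation hazard in Weeks 0 to 8 a multiple of the later one. At 3 times, 1 − KM is 50.2%. At 5 times the later hazard is 0.00974 per week, the cumulative hazard is 5 × 0.00974 × 8 + 0.00974 × 30 = 0.682, and 1 − KM = 49.4%. No median is then reported.

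**The case against.** The strongest reply is that the information is largely present already. If only completers on eow are censored, the final Aalen-Johansen value is essentially the crude proportion escalated, which SAP 10.3 reports together with the number of events. SAP 8.0 tabulates discontinuations by reason. A KM median printed beside fewer than 126 escalations in 252 subjects would be noticed. The endpoint is one of many additional ones, in a single-arm study with no tests. This stands and limits the importance, but nothing in the SAP would explain the discrepancy, and the crude proportion does not correct the percentiles.

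A second reply is that censoring at the last dose is a recognised way to describe escalation while on treatment, so the percentiles are too early only against a different target. That is fair as far as it goes. The SAP does not state that target, and it needs stopping to be unrelated to the chance of escalation, which optional escalation and the listed discontinuation reasons make doubtful. If subjects close to escalating leave first, KM does not reliably describe the hypothetical population either.

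A third reply is that every rate is assumed and constant hazards may be wrong. This also stands. Entry requires completion of Study M14-115, not response, and escalation is open from Week 1, so early escalation is plausible and shrinks the gap.

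A reader might infer that the study will report a misleading median, or that all censoring at last dose is wrong. The documents support neither. The first needs escalation of roughly 40 to 50% with enough stopping, and no rate is given. Censoring eow completers at their last dose is correct.

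**Conclusion.** The point holds as a mismatch between the estimator and what the endpoint appears to describe. The direction follows from the method: subjects who can no longer escalate are treated as still able to, so the percentiles are early for the treated population. The size is conditional. Under constant hazards to Week 38 it runs from negligible (about 5% stopping) to nearly 2 SE with a spurious median (45% escalating, 20% stopping), and it falls if escalation is concentrated early. The impact is modest, because the endpoint is descriptive and not primary. The correction is worth making because it is cheap and removes a foreseeable inconsistency between two results in the same section.

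**What to change.** In SAP 10.3, replace the censoring sentence for this endpoint with wording such as:

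> Permanent discontinuation of study drug before escalation, including death, is a competing event. Subjects who complete treatment on eow without escalation, or whose treatment ends because the sponsor or site terminates the study, are censored at the last dose date. The cumulative incidence of escalation will be estimated by the Aalen-Johansen method with 95% CIs at Weeks 8, 16, 24, 32 and 38. The 25th, 50th and 75th percentiles will be read from this curve and shown as not reached where applicable.

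Keep the product-limit percentiles as a supportive display, labelled as on-treatment estimates that assume stopping is unrelated to the chance of escalation.

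The cost is a few lines of SAP text and one standard estimator on dates already collected. Protocol 8.1.4.2 fixes neither the estimator nor a censoring rule for time-to-event endpoints, so no protocol amendment is needed. The downside is one more display to explain, and percentiles that come out later or not reached.

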10.4 Handling of Multiplicity

Not applicable.

10.5 Efficacy Subgroup Analysis

The subgroups listed below will be used in subgroup analyses of the primary endpoint. The baseline used for the subgroups below is defined as the Study M14-115 Baseline.

- Sex (male, female)
- Age (\leq median, $>$ median)
- Race (white, non-white)
- Baseline fecal calprotectin [\leq median, $>$ median]
- Baseline fecal calprotectin [$\leq 250 \mu\text{g/g}$, $> 250 \mu\text{g/g}$]
- Baseline corticosteroid use (yes, no)

- Baseline immunosuppressant use (yes, no)
- hs-CRP at Baseline (< 10 and \geq 10 mg/L)
- hs-CRP at Baseline (\leq median, $>$ median)
- Crohn's disease activity (CDAI \leq 300, $>$ 300) at Baseline
- Baseline CDAI (\leq median, $>$ median)
- Baseline SES-CD [\leq median, $>$ median]
- Prior infliximab use (yes, no)
- Weight (\leq median, $>$ median)
- Baseline albumin (\leq median, $>$ median)
- Disease duration (< 3 years, $>$ 3 years)
- Disease duration (\leq median, $>$ median)
- Study M14-115 induction dose (higher, standard) [will be performed after Study M14-115 database lock.]

11.0 Safety Analysis

11.1 General Considerations

Laboratory data, AEs, and vital signs are the primary safety parameters in this study. All safety analyses will be performed for Safety population.

The continuous data will be summarized using descriptive statistics, including mean, standard deviation, and median for subjects who have both baseline and post-baseline values by visit. Categorical data will be summarized using frequencies and percentages. The number of non-missing values will also be given.

11.2 Analysis of Adverse Events

The adverse event (AE) will be coded using Medical Dictionary for Regulatory Activities (MedDRA) coding dictionary version 20.0 or later. The analyses of adverse events will be descriptive in nature. All analyses of AEs will be based on the number of patients with AEs (not the number of AEs). Unless otherwise specified, the adverse event will be

summarized by system organ classes (SOCs) and preferred terms (PTs), and presented in the alphabetical order.

11.2.1 Treatment-Emergent Adverse Events

Treatment-emergent AEs (TEAE) are defined as events that begin or worsen either on or after the first dose of the study medication and within 70 days after the last dose of the study drug.

Events where the onset date is the same as the study drug start date are assumed to be treatment-emergent, unless the study drug start time and the adverse event start time are collected and the adverse event start time is prior to the study drug start time. If an incomplete onset date was collected for an adverse event, the event will be assumed to be treatment-emergent unless there is other evidence that confirms that the event was not treatment-emergent (e.g., the event end date was prior to the study drug start date).

11.2.2 Adverse Event Overview

The number and percentage of subjects experiencing TEAEs will be summarized for the following AE categories:

- Any treatment-emergent adverse event
- Any treatment-emergent adverse event that was rated as related (Reasonable Possibility) to study drug by the investigator
- Any treatment-emergent severe adverse event
- Any treatment-emergent serious adverse event
- Any treatment-emergent adverse event leading to discontinuation of study drug
- Any treatment-emergent adverse event leading to death
- Any treatment-emergent adverse event of special interest

11.2.2.1 Adverse Events by System Organ Class and Preferred Term

The number and percentage of subjects experiencing TEAEs will be tabulated by SOC and PT. The SOCs will be presented in alphabetical order, and the PTs will be presented in the alphabetical order within each SOC.

A subject who reports more than one AE in different SOCs will be counted only once in the overall total. A subject who reports two or more different PTs within the same SOC will be counted only once in the SOC total. Subjects reporting more than one AE for a given PT will be counted only once for that PT using the most extreme incident (i.e., most "severe" for the severity tables and most "related" for the relationship tables).

11.2.2.2 Adverse Events by Maximum Severity

TEAEs will also be summarized by maximum severity. If a subject has an AE with an unknown severity, then the subject will be counted in the severity category of unknown, even if the subject has another occurrence of the same event with a severity present. The only exception is if the subject has another occurrence of the same AE with the most extreme severity – severe. In this case, the subject will be counted under the severe category.

11.2.2.3 Adverse Events by Maximum Relationship

TEAEs will also be summarized by maximum relationship as assessed by the investigator. If a subject has an AE with an unknown relationship, then the subject will be counted in the relationship category of "unknown," even if the subject has another occurrence of the same event with a relationship present. The only exception is if the subject has another occurrence of the same AE with a relationship assessment of "Reasonable Possibility. In this case, the subject will be counted under the "Reasonable Possibility" category.

11.2.2.4 Serious Adverse Events (Including Deaths) and Adverse Events Leading to Study Drug Discontinuation

All pre- and post-treatment serious adverse events (TESAEs), deaths, and AEs leading to discontinuation of study drug will be listed. The number and percentage of subjects experiencing SAEs (including deaths) and AEs leading to discontinuation of study drug will be tabulated.

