6.3 Relationship to Study Drug

The investigator will use the following definitions to assess the relationship of the AE to the use of study drug:

Reasonable Possibility	An adverse event where there is evidence to suggest a causal relationship between the study drug and the adverse event.
-------------------------------	-------------------------------------------------------------------------------------------------------------------------

No Reasonable Possibility	An adverse event where there is no evidence to suggest a causal relationship between the study drug and the adverse event.
----------------------------------	----------------------------------------------------------------------------------------------------------------------------

For causality assessments, events assessed as having a reasonable possibility of being related to the study drug will be considered "associated." Events assessed as having no reasonable possibility of being related to study drug will be considered "not associated." In addition, when the investigator has not reported a causality or deemed it not assessable, AbbVie will consider the event associated.

If an investigator's opinion of no reasonable possibility of being related to study drug is given, an Other cause of event must be provided by the investigator for the SAE.

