8.1.5 Statistical Analyses of Safety

Laboratory data, AEs, and vital signs are the primary safety parameters in this study. All safety analyses will be performed using the Safety set, which includes all subjects who enrolled into this study and received at least one dose of study drug. Treatment-emergent AEs are defined as events that begin or worsen either on or after the first dose of the study drug and within 70 days after the last dose of the study drug. An overview of treatment-emergent AEs, including AEs of special interest such as AEs leading to death and AEs leading to premature discontinuation (see details in the SAP), AEs by Medical Dictionary for Drug Regulatory Activities (MedDRA version 15.1 or later) preferred term and system organ class, AEs by maximum relationship to study drug, and AEs by maximum severity will be summarized by number and percentage.

Changes in laboratory data will be described using statistical characteristics. In addition, shift tables and listings will be provided for abnormal values, whereby the normal range of the analyzing laboratory will be used. Vital signs will be analyzed similarly.

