11.2.2.6 Reasonably Possibly Related Adverse Events by System Organ Class and Preferred Term

Reasonable Possibility TEAEs will be summarized by SOC and PT.

11.2.2.7 Reasonably Possibly Related Serious Adverse Events by System Organ Class and Preferred Term

Reasonable Possibility serious TEAEs will be summarized by SOC and PT.

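### Does the SAP undercount drug-related adverse events by tabulating unrated causality as 'unknown' when the protocol treats it as associated?

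*SAP*

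**What the plan says.** Protocol section 6.3 has the investigator rate each adverse event as Reasonable Possibility or No Reasonable Possibility. The first class is called associated, the second not associated. It adds that "when the investigator has not reported a causality or deemed it not assessable, AbbVie will consider the event associated". Protocol section 8.1.5, which specifies the safety analysis, asks only that "AEs by maximum relationship to study drug, and AEs by maximum severity will be summarized by number and percentage".

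The SAP uses relationship in four outputs:

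- **Overview (11.2.2).** One row is "Any treatment-emergent adverse event that was rated as related (Reasonable Possibility) to study drug by the investigator". Section 11.2.2.9 gives the overview rows as event rates per 100 patient-years as well.
- **Maximum relationship (11.2.2.3).** The basis is stated: "TEAEs will also be summarized by maximum relationship as assessed by the investigator". For missing ratings, "If a subject has an AE with an unknown relationship, then the subject will be counted in the relationship category of" 'unknown'. The only exception is another occurrence of the same event rated Reasonable Possibility.
- **Related events (11.2.2.6).** "Reasonable Possibility TEAEs will be summarized by SOC and PT".
- **Related serious events (11.2.2.7).** "Reasonable Possibility serious TEAEs will be summarized by SOC and PT".

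SAP section 12.1, which lists differences from the protocol, covers efficacy variables and the Bristol Stool Scale. It does not mention adverse-event relationship.

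**The concern.** By the sponsor's own definition an unrated event belongs with the related events, yet none of the four outputs puts it there. Related counts under the SAP can therefore equal or fall below those under protocol 6.3, but never exceed them. Safety is part of the primary objective, so an undeclared difference in the less cautious direction deserves a look. Two details add to the impression. The SAP does not say what an unknown relationship is, although protocol 6.3 names two cases (not reported and not assessable). And for another incomplete adverse-event item the SAP takes the inclusive default: "If an incomplete onset date was collected for an adverse event, the event will be assumed to be treatment-emergent unless there is other evidence" to the contrary.

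**Working it through.** **Step 1. Compare the two rules case by case.** Take one subject and one preferred term, and read 'unknown' as not reported or not assessable. RP is Reasonable Possibility and NRP is No Reasonable Possibility.

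| Occurrences | Protocol 6.3 | SAP 11.2.2.3 |
|---|---|---|
| unrated only | associated | unknown |
| unrated and NRP | associated | unknown |
| unrated and RP | associated | RP |
| RP, with or without NRP | associated | RP |
| NRP only | not associated | NRP |

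The labels differ in the first two rows, so the textual difference is real.

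**Step 2. See whether the protocol 6.3 count is lost.** The SAP ranks RP above 'unknown' and 'unknown' above NRP, and each subject falls in one category per preferred term. In the table, every associated case is RP or unknown, and no other case is. Hence, for each preferred term:

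subjects associated under protocol 6.3 = subjects in RP + subjects in 'unknown'.

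The planned table yields the count by one addition. Two quantities cannot be read off in this way: the related serious count and the related event rate per 100 patient-years. Unrated serious events still appear in the serious-event tabulation (11.2.2.4) and listing (11.2.2.10).

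**Step 3. Bound the effect on the related percentage.** SAP section 4.2 gives 252 enrolled subjects, so the Safety set is at most 252. A subject with an unrated event and no event rated related moves the percentage by at least 1/252. The number of such subjects is not in the documents, so the following range is assumed:

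| Subjects | Change at 252 subjects (percentage points) |
|---|---|
| 0 | 0 |
| 1 | 1/252 = 0.40 |
| 3 | 3/252 = 1.19 |
| 5 | 5/252 = 1.98 |
| 10 | 10/252 = 3.97 |

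**Step 4. Bound the effect on the related event rate.** Exposure runs from first dose through last dose plus 70 days (SAP 9.1). The last dose is at Week 38 for every-other-week dosing or Week 39 for weekly dosing (protocol 5.5.1). With every dose taken on schedule:

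- all every other week: 38 × 7 + 1 + 70 = 337 days; 252 × 337 / 365.25 = 232.5 patient-years; one event = 100 / 232.5 = 0.43 per 100 patient-years.
- all weekly: 39 × 7 + 1 + 70 = 344 days; 252 × 344 / 365.25 = 237.3 patient-years; one event = 100 / 237.3 = 0.42 per 100 patient-years.

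Shorter exposure or fewer treated subjects makes each event weigh more, so about 0.42 is the minimum per event. These figures are weights per subject and per event. They are not evidence that any event is unrated.

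**Step 5. Look for the SAP's own convention.** Section 11.2.2.2 treats unknown severity in the same way: counted as 'unknown' unless another occurrence of the event has the top category. Section 11.2.2.3 follows that pattern. It is a closer parallel than the onset-date rule, which decides whether an event is treatment-emergent and not how it is rated.

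**The case for a change.** The strongest case for acting is that protocol 6.3 does not confine its rule to expedited reporting. It is given for causality assessments in general, so a reader could expect at least one table to follow it, or a line in SAP 12.1 saying that none does. The overview row has no 'unknown' category beside it, and the tables in 11.2.2.6 and 11.2.2.7 do not repeat that the rating is the investigator's. A definition and a footnote would cost almost nothing.

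Part of this stands. SAP 12.1 is silent, 'unknown' is undefined, and the related serious count and related event rate under protocol 6.3 cannot be derived from the planned tables. But protocol 6.3 says how the sponsor regards an event and does not say how tables are built. Protocol 8.1.5 leaves missing causality open, and protocol 8.1 leaves the details of analysis to the SAP. Tabulating the investigator's rating, with missing ratings shown as a category of their own, is a legitimate way to fill that space. For 11.2.2.6 and 11.2.2.7 the point rests on silence: the text neither adds unrated events nor excludes them in words.

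**Conclusion.** The difference in wording is real, but the plan needs no change. Followed as written, the SAP gives sound descriptive tables. The overview row and the maximum-relationship table are labelled as investigator-rated. Unrated events stay visible in the 'unknown' category, and the protocol 6.3 subject count for each preferred term follows by addition. No statistical test depends on these counts.

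The effect may be nil, because protocol section 6.0 requires the investigator to record a relationship for every adverse event. Otherwise it is at least 0.40 percentage points per affected subject and at least about 0.42 per 100 patient-years per unrated event. Parallel related-event outputs would duplicate the existing ones for a category that may be empty.

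The conclusion assumes that 'unknown' covers exactly the two cases in protocol 6.3, which is the natural reading, and that unrated events are few. Should many turn up, the 'unknown' category would show it.
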